9.4 Data Processing

All data will be entered by site personnel into the eCRF (as detailed in Section 9.2.1).

The data-review and data handling document, to be developed during the initiation phase of the study, will include specifications for consistency and plausibility checks on data and will also include data handling rules for obvious data errors. Query/correction sheets for unresolved queries will be sent to the study monitors for resolution with the Investigator. The database will be updated on the basis of signed corrections.

Previous and concomitant medications will be coded using the latest available version of World Health Organisation - Drug Dictionary (WHO-DD). Medical history/current medical conditions and AEs will be coded using the latest available version of Medical Dictionary for Regulatory Activities (MedDRA) terminology.

Previous and concomitant diseases as well as AEs will be coded with latest available version of MedDRA.

The versions of the coding dictionaries will be provided in the CSR.

9.5 Archiving Study Records

According to International Council for Harmonisation (ICH) guidelines, essential documents should be retained for a minimum of 2 years after the last approval of a marketing application in an ICH region and until there are no pending or contemplated marketing applications in an ICH region or at least 2 years have elapsed since the formal discontinuation of clinical development of the study drug. However, these documents should be retained for a longer period if required by the applicable legal requirements.

9.6 Good Clinical Practice

The procedures set out in this study protocol are designed to ensure that AstraZeneca and Investigator abide by the principles of the Good Clinical Practice (GCP) guidelines of the ICH, and of the Declaration of Helsinki (2013) [1]. The study also will be carried out in keeping with local legal requirements.

9.7 Informed Consent

Before each patient is admitted to the study, informed consent will be obtained from the patient according to the regulatory and legal requirements of the participating country. This Informed consent form (ICF) must be dated and retained by the Investigator as part of the study records. The Investigator will not undertake any investigation specifically required only for the clinical study until valid consent has been obtained. The terms of the consent and when it was obtained must also be documented in the eCRF.

If a protocol amendment is required, the ICF may need to be revised to reflect the changes to the protocol. If the ICF is revised, it must be reviewed and approved by the appropriate IEC/IRB, and signed by all patients subsequently enrolled in the study as well as those currently enrolled in the study.

9.8 Protocol Approval and Amendment

Before the start of the study, the study protocol and/or other relevant documents will be approved by the IEC/IRB/Competent Authorities, in accordance with local legal requirements. AstraZeneca must ensure that all ethical and legal requirements have been met before the first patient is enrolled in the study.

This protocol is to be followed exactly. To alter the protocol, amendments must be written and approval obtained from the appropriate personnel and IRB/IEC/Competent Authority prior to implementation (if appropriate).

Administrative changes (not affecting the patient benefit/risk ratio) may be made without the need for a formal amendment. All amendments will be distributed to all protocol recipients, with appropriate instructions.

9.9 Duration of the Study

For each individual patient, the maximum duration of the study will be up to 62 days (including up to 6 weeks for Screening and Run-in Period, 2-week Treatment Period, and 5-day Follow-up Period, and 1 additional day for allowed window periods).

The study will close when all patients have completed the last visit (Visit 10).

9.10 Premature Termination of the Study

9.10.1 Stopping Rules for an Individual Patient

Withdrawal criterial for an individual patient are specified in Section 4.5.

9.10.2 Stopping Rules for the Study

If the Investigator, AstraZeneca, or the medical monitor becomes aware of conditions or events that suggest a possible hazard to patients if the study continues, the study may be terminated after appropriate consultation between the relevant parties. The study may also be terminated early at AstraZeneca's discretion in the absence of such a finding.

Conditions that may warrant termination include, but are not limited to:

- The discovery of an unexpected, significant, or unacceptable risk to the patients enrolled in the study.
- Failure to enroll patients at an acceptable rate.
- A decision on the part of AstraZeneca to suspend or discontinue development of the study drug.

9.11 Confidentiality

All study findings and documents will be regarded as confidential. The Investigator and members of his/her research team must not disclose such information without prior written approval from AstraZeneca.

The anonymity of participating patients must be maintained. Patients will be identified on eCRFs and other documents submitted to PAREXEL by their patient number, not by name. Documents not to be submitted to PAREXEL that identify the patient (eg, the signed informed consent) must be maintained in confidence by the Investigator.

11 APPENDICES

11.1 Additional Safety Information

FURTHER GUIDANCE ON THE DEFINITION OF A SERIOUS ADVERSE EVENT (SAE)

Life-threatening

'Life-threatening' means that the subject was at immediate risk of death from the AE as it occurred or it is suspected that use or continued use of the product would result in the subject's death. 'Life-threatening' does not mean that had an AE occurred in a more severe form it might have caused death (eg, hepatitis that resolved without hepatic failure).

Hospitalisation

Outpatient treatment in an emergency room is not in itself a serious AE, although the reasons for it may be (eg, bronchospasm, laryngeal oedema). Hospital admissions and/or surgical operations planned before or during a study are not considered AEs if the illness or disease existed before the subject was enrolled in the study, provided that it did not deteriorate in an unexpected way during the study.

Important Medical Event or Medical Intervention

Medical and scientific judgement should be exercised in deciding whether a case is serious in situations where important medical events may not be immediately lifethreatening or result in death, hospitalisation, disability or incapacity but may jeopardise the subject or may require medical intervention to prevent one or more outcomes listed in the definition of serious. These should usually be considered as serious.

Simply stopping the suspect drug does not mean that it is an important medical event; medical judgement must be used.

- Angioedema not severe enough to require intubation but requiring intravenous hydrocortisone treatment.
- Hepatotoxicity caused by paracetamol (acetaminophen) overdose requiring treatment with N-acetylcysteine.
- Intensive treatment in an emergency room or at home for allergic bronchospasm.
- Blood dyscrasias (eg, neutropenia or anaemia requiring blood transfusion, etc.) or convulsions that do not result in hospitalisation.
- Development of drug dependency or drug abuse.

A Guide to Interpreting the Causality Question

When making an assessment of causality, consider the following factors when deciding if there is a 'reasonable possibility' that an AE may have been caused by the drug.

• Time Course. Exposure to suspect drug. Has the subject actually received the suspect drug? Did the AE occur in a reasonable temporal relationship to the administration of the suspect drug?

- Consistency with known drug profile. Was the AE consistent with the previous knowledge of the suspect drug (pharmacology and toxicology) or drugs of the same pharmacological class? Or could the AE be anticipated from its pharmacological properties?
- De-challenge experience. Did the AE resolve or improve on stopping or reducing the dose of the suspect drug?
- No alternative cause. The AE cannot be reasonably explained by another aetiology such as the underlying disease, other drugs, other host or environmental factors.
- Re-challenge experience. Did the AE reoccur if the suspected drug was reintroduced after having been stopped? AstraZeneca would not normally recommend or support a re-challenge.
- Laboratory tests. A specific laboratory investigation (if performed) has confirmed the relationship?

In difficult cases, other factors could be considered such as:

- Is this a recognised feature of overdose of the drug?
- Is there a known mechanism?

Causality of 'related' is made if following a review of the relevant data, there is evidence for a 'reasonable possibility' of a causal relationship for the individual case. The expression 'reasonable possibility' of a causal relationship is meant to convey, in general, that there are facts (evidence) or arguments to suggest a causal relationship.

The causality assessment is performed based on the available data including enough information to make an informed judgement. With limited or insufficient information in the case, it is likely that the event(s) will be assessed as 'not related'.

Causal relationship in cases where the disease under study has deteriorated due to lack of effect should be classified as no reasonable possibility.

11.2 International Airline Transportation Association (IATA) 6.2 Guidance Document

Labelling and shipment of biohazard samples

International Airline Transportation Association (IATA) classifies biohazardous agents into 3 categories

(http://www.iata.org/whatwedo/cargo/dangerous_goods/infectious_substances.htm). For transport purposes the classification of infectious substances according to risk groups was removed from the Dangerous Goods Regulations in the 46th edition (2005). Infectious substances are now classified either as Category A, Category B or Exempt. There is no direct relationship between risk groups and categories A and B.

Category A Infectious Substances are infectious substances in a form that, when exposure to it occurs, is capable of causing permanent disability, life-threatening or fatal disease in otherwise healthy humans or animals. Category A pathogens are eg, Ebola, Lassa fever virus:

• are to be packed and shipped in accordance with IATA Instruction 602.

Category B Infectious Substances are infectious Substances that do not meet the criteria for inclusion in Category A. Category B pathogens are e.g., hepatitis A, B, C, D, and E viruses, human immunodeficiency virus (HIV) types 1 and 2. They are assigned the following UN number and proper shipping name:

- UN 3373 Biological Substance, Category B
- are to be packed in accordance with UN3373 and IATA 650

Exempt - all other materials with minimal risk of containing pathogens

- Clinical trial samples will fall into Category B or exempt under IATA regulations
- Clinical trial samples will routinely be packed and transported at ambient temperature in IATA 650 compliant packaging (http://www.iata.org/whatwedo/cargo/dangerous_goods/infectious_substances. htm)
- Biological samples transported in dry ice require additional dangerous goods specification for the dry-ice content
- IATA compliant courier and packaging materials should be used for packing and transportation and packing should be done by an IATA certified person, as applicable
- Samples routinely transported by road or rail are subject to local regulations which require that they are also packed and transported in a safe and appropriate way to contain any risk of infection or contamination by using approved couriers and packaging / containment materials at all times. The IATA 650 biological sample containment standards are encouraged wherever possible when road or rail transport is used.

MedDRA	Medical Dictionary for Regulatory Activities
mEq	milliequivalent
min	minute
mL	millilitre
mmHg	millimetres of mercury
n	number of patients
NA	not applicable
ND	not determined
NQ	not quantifiable
CCI	
PK	pharmacokinetic(s)
PT	preferred term
CCI	
SAE	serious adverse event
SAP	statistical analysis plan
SD	standard deviation
SOC	system organ class
SOP	standard operating procedure
ST	Start of treatment
T2DM	type 2 diabetes mellitus
TLFs	tables, listings and figures
UACR	urine albumin to creatinine ratio
CCI	
WHO-DD	World Health Organisation - Drug Dictionary

STATISTICAL ANALYSIS PLAN

The Statistical Analysis Plan (SAP) details the statistical methodology to be used in analysing study data and outlines the statistical programming specifications for the Tables, Listings and Figures (TLFs). It describes the variables and analysis sets, anticipated data transformations and manipulations and other details of the analyses not provided in the Clinical Study Protocol (CSP).

The analyses described are based on the CSP Version 5.0, dated 23 April 2018. The SAP will be finalised prior to database lock and describes the statistical analysis as it is foreseen when the study is being planned. If circumstances should arise during the study rendering this analysis inappropriate, or if improved methods of analysis should arise, updates to the analyses may be made in an updated SAP. Any deviations from the SAP after database lock, reasons for such deviations and all alternative or additional statistical analyses that may be performed, will be described in a SAP Addendum and discussed in the Clinical Study Report (CSR).

The SAP describes Group 1 as it was originally planned in the latest version of the CSP. it was decided that no Group 1 subjects will be enrolled onto this study (please see reference in Action log on the 22nd of March 2019), so no statistical outputs will contain Group 1 information.

1. STUDY OBJECTIVES

1.1 Primary Objective

The primary objective is to investigate the change in 24-hour sodium excretion during dapagliflozin treatment between Baseline (average of Days -3 to -1) and average of Days 2 to 4 within each study group.

- Patients with type 2 diabetes mellitus (T2DM) with impaired renal function;
- Patients with T2DM with preserved renal function;
- Non-diabetic patients with impaired renal function.

1.2 Secondary Objectives

The secondary objectives of the study, to be assessed for each of the groups, are to:

- Evaluate the change in 24-hour sodium excretion from Baseline to end of treatment, and during follow-up;
- Evaluate the change in 24-hour glucose excretion;
- Evaluate the change in mean 24-hour systolic blood pressure;
- Evaluate the change in plasma volume;
- Evaluate the change in extracellular volume;
- Evaluate the pharmacokinetics of dapagliflozin;
- Evaluate the change in 24-hr urine albumin to creatinine ratio (UACR).

1.4 Safety Objectives

The safety objectives are to evaluate the safety and tolerability of dapagliflozin in each of the target patient populations.

2. STUDY DESIGN

DAPASALT is an open label, mechanistic, three-arm study to evaluate the natriuretic effect of two-week dapagliflozin treatment in T2DM patients with either preserved or impaired renal function and in non-diabetics with impaired renal function.

The study population will comprise three groups of patients:

- Group 1: T2DM patients with impaired renal function, defined as having an estimated glomerular filtration rate (eGFR), defined by Chronic Kidney Disease (CKD) Epidemiology Collaboration (CKD-EPI), of ≥ 25 and ≤ 50 millilitres/minute/1.73 metres squared (mL/min/1.73m²);
- Group 2: T2DM patients with preserved renal function, defined as having an eGFR, defined by CKD-EPI, of > 90 and ≤ 130 mL/min/1.73 m² for patients aged 59 years

- or younger, between >85 and \leq 130 mL/min/1.73 m² for patients aged 60 to 69 years, and between >75 and \leq 130 mL/min/1.73 m² for patients aged 70 years or older;
- Group 3: Non-diabetic patients with impaired renal function, defined as eGFR range for Group 1.

A total of 51 patients are planned to be enrolled in the study, with 17 patients in each group.

The study periods and schedule of visits are presented in Section 7.1 (Tables 5 and 6) of CSP. Briefly, the efficacy measurements will, with some exceptions, be collected four times during the course of the study: Visit 4 (day 1 relative to start of treatment), Visit 5 (day 4), Visit 8 (typically, day 14) and Visit 9 (typically, day 18), with the final time point being post-treatment. A notable exception is the 24-hour urine, which will be collected on three, or four, consecutive days during four time periods, with the last day in these periods being day -1, day 4, day 14 and day 17, and 24-hr blood pressure, which will be collected at Visit 7 (typically, day 13) rather than day 14. Blood samples to evaluate pharmacokinetic (PK) properties of dapagliflozin in this population will be taken twice during the study, once during Visit 5 (predose) and four times during Visit 8 (pre-dose and 1, 2, 4 h post-dose). Additional bioimpedence spectroscopy measurements will be performed at the same time as PK sampling during Visit 8.

Adverse events (AE), including serious adverse events (SAE) are collected throughout the study, with SAE collection starting at the screening visit and AE collection at dosing, both ending at the last visit (Visit 10, typically day 19). Laboratory safety assessments will generally be done at Screening (Visit 1), Visit 4 and Visit 8 (See Section 5.1.3.2), with some exceptions.

As many of the efficacy measurements will be taken at four distinctive time periods during the course of the study, namely baseline, soon after treatment start, at the end of treatment and at the end of follow up, when reporting the efficacy results of the study each measurement will be assigned to an analysis window:

- **Baseline** is the measurement obtained before initiation of treatment, typically during Visit 4. For 24-hr blood pressure, the baseline measurement is the measurement obtained the day before Visit 4.
- Start of Treatment (ST) is the measurement obtained after the patient has been in the study for a short time, typically on Visit 5.
- End of treatment (ET) is the measurement obtained on the visit corresponding to the last day of the treatment period, namely Visit 8, unless the patient attended an early termination visit. For 24-hr blood pressure, as well as CCI measurements in the 24-hr urine, the end of treatment measurement is the measurement obtained the day before Visit 8.

• Follow-up (FU) is the measurement obtained after the end of the treatment period, namely Visit 9. CC

The exception from the rules outlined above is the 24-hr urine, the collection of which will take place on consecutive days, rather than on one single day. In this case, Baseline, ST, ET and FU used in the analyses will be the averages of these consecutive samples. Explicitly, Baseline is the average of measurements obtained on day -3 to day -1, ST the average of measurements obtained on day 2 to day 4, ET the average of measurements obtained on day 12 to day 14 and FU the average of measurements obtained on day 15 to day 17.

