On Day 1 (Dosing Initiation Visit), patients will start the administration of one dapagliflozin 10 mg tablet per day. Patients will continue with dapagliflozin until Day 14, following which they will enter a Follow-up Period from Day 15 to Day 19.

During the Treatment Period, the following clinic visits are scheduled: Visit 4 (Day 1: Dosing Initiation Visit), Visit 5 (Day 4), Visit 6 (Day 5), Visit 7 (Day 13) and Visit 8 (Day 14: end of treatment). There will be 4 consecutive 24-hr urine collections on Days 1, 2, 3, and 4 followed by 3 consecutive 24-hr urine collections on Days 12, 13, and 14. Initiation of 24-hr blood pressure monitoring will be done on Days 4 and 13.

Plasma volume assessment and bioimpedance spectroscopy for extracellular volume,

CCI	will be performed on Days 1, 4 and 14. On
Day 1, CCI , plasm	a volume and bioimpedance spectroscopy
measurements will be done prior to the fir	st dose of dapagliflozin. CCI

Blood samples for pharmacokinetics of dapagliflozin will be collected on Days 4 and 14.

A window period of ± 1 day is allowed for Visit 7 at Day 13. Urine collection on Day 12 should start 1 day before Visit 7. Visit 8 will occur 1 day after Visit 7 and the follow-up period of 5 days (Day 15 to Day 19) will start 1 day after Visit 8.

Follow-up Period (Day 15 to Day 19):

On Day 15, treatment with dapagliflozin will be discontinued (last dose to be taken on Day 14) and patients will enter a 5-day Follow-up Period between Day 15 and Day 19. A clinic visit is scheduled on Day 18 to provide the last 24-hr urine samples and participate in the investigations detailed in Table 5 and Table 6. CC

. The patients will return to the clinic for the last study visit on Day 19 and return equipment provided.

There will be 3 consecutive 24-hr urine collections on Days 15, 16, and 17. On Day 18, 24-hr blood pressure monitoring will be initiated. Plasma volume assessment and bioimpedance spectroscopy for extracellular volume, **CC**

will be performed as well.

After the end of the study, patients will return to their normal clinical care plan.

Stopping rules for individual patients are described in Section 4.5. Stopping rules for the study are described in Section 9.10.

The study design is presented in Figure 1. Refer to the Study Plan (Table 5 and Table 6) for further details of the timings of planned assessments.

Figure 1: Study Design

T2DM=Type 2 diabetes mellitus

Note: lines indicate days on which 24-hr urine is collected.

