- f. Telephone call by dietician within 24 hours as a reminder for food boxes to be consumed from Day -20 (at the earliest) onwards and to complete food questionnaire. Dietary advice and food boxes with a daily sodium content of approximately 150 mmol sodium content will start at Day -20 at the earliest and continue throughout the study (until Visit 9).

AstraZeneca AB	Clinical Study Protocol
Study code: D1690C00049	CONFIDENTIAL
Investigational product: Dapagliflozin	

g. During the Run-in Period, there will be regular contacts between Investigators and patients to ensure that their blood glucose is adequately controlled and to confirm that their insulin regime remains stable while on food boxes. Patient consultation with Investigator may occur at several times from Day -20 to Day -1. Exact dates will be decided on an as needed basis by patient and Investigator. Patients may have their insulin requirements adjusted according to the caloric content of the food boxes, if needed.

h.

Samples should be obtained prior to dosing. At the Screening Visit and on Day 14, all safety laboratory assessments specified in Table 3 will be performed; on Day 1, only haemoglobin, creatinine, haematocrit, glucose will be assessed; and on Day 4 and Day 18, only creatinine, haematocrit, glucose will be assessed. At the Screening Visit HbA1c will be assessed for confirmation of inclusion criterion.

- j. On Day 4, a single pre-dose sample will be obtained. On Day 14, samples will be obtained pre-dose, 1, 2 and 4 hrs post-dose.
- CCI
- 1. Urine dipstick parameters to be evaluated are blood, glucose and albumin.
- CCI
- n. A positive urine pregnancy test (dipstick analysed at the study centre) should be confirmed with a serum pregnancy test.
- o. Patients will be given instructions on how to collect and store 24-hr urine samples. From the 24-hr urine samples, following parameters will be analysed at all timepoints: 24-hr CC glucose, sodium, CC and UACR; and

will be analysed only on Days -1, 4, 14, and 17. For premenopausal women, the Investigator will estimate the menstrual timing and aim to avoid the 2 urine collection periods (Day -3 to 4 and Day 12 to 17) during menstruation. For the second collection period (Day 12 to 17), the urine collection will start 1 day before Visit 7 (Day 13 ± 1 day) and end 4 days after Visit 7 (Day 13 ± 1 day).

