8.3 Efficacy Analyses

The Baseline for 24-hr urinary related endpoints is the average of the daily urinary sodium excretion from Days -3, -2 and -1 assessments prior to the date of the first dose of the study treatment (with the exception of **CC** for which the Baseline is the urinary assessment from Day -1).

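### SAP end-of-treatment rule for certain redacted 24-hr urine measurements points to Day 13, which is either not an assay day for them or at odds with the Day 12–14 average

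*SAP*

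**What the plan says.** **The SAP window.** The end-of-treatment (ET) definition in SAP section 2 makes an exception for 24-hr blood pressure and for some redacted items: "measurements in the 24-hr urine, the end of treatment measurement is the measurement obtained the day before Visit 8". The same section places "Visit 8 (typically, day 14"), so the rule means Day 13. The paragraph after the window definitions then treats 24-hr urine as the exception to all of them and takes ET as the mean of Days 12 to 14. No visible words exempt the redacted items from that averaging.

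**The protocol assay schedule.** Protocol section 7.1 (Table 5 footnote o, Table 6 footnote m) divides the 24-hr urine analytes in two. For glucose, sodium, urine albumin:creatinine ratio (UACR) and some redacted items, the "following parameters will be analysed at all timepoints". A second set, fully redacted, "will be analysed only on Days -1, 4, 14, and 17".

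**Single-day items.** Protocol section 8.3 exempts a redacted urinary item from the three-day Baseline, "for which the Baseline is the urinary assessment from Day -1". SAP section 2 describes the urine periods "with the last day in these periods being day -1, day 4, day 14 and day 17", the same four days as the restricted assay schedule.

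**The concern.** The SAP rule and the protocol's restricted schedule name different days at the end of treatment. If both concern the same analytes, the SAP asks for a result that is not scheduled to be produced, and the Day 14 result that is produced falls outside the stated window.

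ET enters two of the three within-patient contrasts that SAP Appendix B lists for each such measurement: ET minus Baseline, and follow-up (FU) minus ET. In SAP section 5.3.16.1 it is one of the two time points in Model 1 and one end of the change in Model 2. Appendix D does not impute missing efficacy data. A programmer following the text would output an empty ET column or substitute Day 14 without a written rule.

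**Working it through.** The plan states no figure to reproduce. The check maps visits to collection labels and compares them with the assay days.

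**Inputs**
- Visit 7 = Day 13 + s, with s = -1, 0 or +1 (Protocol 3.1).
- "Visit 8 will occur 1 day after Visit 7" (Protocol 3.1), so Visit 8 = Day 14 + s.
- Urine labels in the second period follow Visit 7: "the urine collection will start 1 day before Visit 7 (Day 13 ± 1 day) and end 4 days after Visit 7" (Protocol 7.1). Hence label = actual day - s.
- Restricted-panel assay days: -1, 4, 14, 17 (Protocol 7.1).

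**Step 1: the visit window**

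| s | Visit 7 | Visit 8 | Day before Visit 8 (actual) | Collection label | Collected? | Restricted-panel assay day? |
|---|---|---|---|---|---|---|
| -1 | 12 | 13 | 12 | 12 - (-1) = 13 | yes | no |
| 0 | 13 | 14 | 13 | 13 - 0 = 13 | yes | no |
| +1 | 14 | 15 | 14 | 14 - 1 = 13 | yes | no |

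The window does not remove the mismatch, because Visit 8 and the urine labels both move with Visit 7. Only if labels were read as strict calendar days would the s = +1 patients match Day 14, and the Visit 7 anchoring speaks against that reading.

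**Step 2: hand-over date.** Reading the rule as the date a sample is handed in does not help. Visit 7 receives the Day 12 collection, Visit 8 receives Day 13, and the Day 14 collection starts at Visit 8 and is handed in at Visit 9 (Protocol 7.2.3.4, 7.2.3.5, 7.2.4.1).

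**Step 3: the other time points.** The day before Visit 4 (Day 1) is Day -1, and the day before Visit 9 (Day 18) is Day 17. Both are assay days. Day 4 is the collection started at Visit 5. Day 14, the collection started at Visit 8, fits the same pattern. Among these, only the SAP's ET day is out of line.

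**Step 4: the two cases**
- *Case A: the SAP items are the restricted panel.* Day 13 is not one of the four assay days. A Day 13 urine is collected, but no assay of this panel is scheduled on it. Contrasts needing ET: ET - Baseline and FU - ET, i.e. 2 of 3. Model 1 keeps one of its two time points.
- *Case B: the SAP items are assayed daily.* A Day 13 value exists, but ET has two visible definitions in one section: Day 13 alone, and the mean of Days 12, 13 and 14.

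**Step 5: which case is more likely.** Case A. A redacted urinary item has a Day -1-only Baseline, the restricted panel is the one without daily values to average, and redacted urinalysis rows in Tables 5 and 6 are marked on Days -1, 4, 14 and 17.

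**The case against.** The strongest objection is that the link between the two documents is blacked out. The analyte names are redacted in SAP section 2, in both protocol footnotes and in protocol section 8.3. The daily panel also contains redacted items, and those would have a Day 13 value. Text that might settle the day for each analyte is not visible either: SAP section 5.1.5.3 (cited in 5.3.16.3), section 5.3.17, and the definitions announced at the end of Appendix B. Redacted text cannot be counted as absent from the plan. All of this stands, and it makes the point conditional.

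Second, in Case B a sentence naming particular analytes can be read as a specific exception to the averaging rule, much as protocol section 8.3 does for Baseline. That is a fair reading, but the averaging paragraph presents itself as the exception to the windows above it, so the visible text does not settle which prevails.

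Third, if the averaging paragraph prevails in Case A, a mean over Days 12 to 14 of whatever is available reduces to the Day 14 value. That gives a usable result, but only by disregarding the urine clause, so the clause still needs correcting.

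Fourth, no data are lost: Day 14 is assayed, and an empty ET column would be noticed at once. This stands and limits the seriousness.

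**Conclusion.** The point holds in conditional form. What is certain is that the SAP rule resolves to the collection labelled Day 13 for every permitted timing of Visit 7, and that one redacted protocol panel is assayed on Day 14 and not on Day 13. What is inferred is that the two refer to the same analytes. If so, ET has no scheduled assay and 2 of 3 contrasts cannot be computed as written. If not, the section gives two ET definitions without saying which takes precedence.

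A reader might infer that the ET value is missing in every patient and that these contrasts are lost. The documents do not support that as a plain statement. It depends on the redacted identity of the analytes, a Day 13 urine is collected, and a Day 14 assay exists from which the contrasts could be formed under a corrected rule.

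The scope is narrow. The primary endpoint (sodium, Days 2 to 4) and the visible urine secondary endpoints (sodium, glucose, UACR) are assayed at every collection and have their own stated windows. The Day 13 rule is also consistent for 24-hr blood pressure. Only redacted 24-hr urine measurements can be affected.

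**What to change.** The sponsor can see the analyte names and can determine at once which case applies. In SAP section 2:
- Keep the day-before-Visit-8 rule for 24-hr blood pressure only.
- For any 24-hr urine analyte assayed only on Days -1, 4, 14 and 17, define ET as the collection started at Visit 8 (nominal Day 14), and exempt it explicitly from the averaging paragraph.
- For any analyte assayed daily, use the Day 12–14 mean, or state the single-day exception and that it overrides the mean.

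The cost is one SAP sentence and one derivation rule, with no new samples or assays. It is best done before database lock. After lock, the SAP's introduction requires any departure to be described in an addendum and discussed in the study report.
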